The primary outcome is the proportion of participants assigned to each incentive amount that consent to enroll in each of the two parent RCTs.

b. Primary analytic sample

Intention-to-treat (ITT) approach such that the analytic sample will include all patients randomized in the RETAIN trial, even if ultimately deemed ineligible for the parent trials.

c. Primary analysis

We will first assess bivariate relationships of incentives with the primary outcome using chi-square tests for comparisons of proportions. To examine the hypothesized statistical interactions, we will use logistic, linear, or quantile regression, as appropriate based on outcome parameterizations and distributions. In the above analyses we treated incentive as an ordered variable. In all analyses in which the parent trial enrolls in multiple centers, we will model the center from which patients are recruited as a fixed effect, thereby mitigating confounding by center and adjusting variance estimates for clustering of participants within centers. To adjust for chance covariate imbalance among arms, primary analyses will include covariates (see Table 1) in multivariable models if they are significantly associated with the intervention arm and predictive of enrollment in the parent trials in bivariate analyses. To avoid problems in estimating odds ratios due to sparse data, we will limit the number of covariates to no more than 1 per 10 participants enrolling in the parent trials. In all analyses related to the BASC parent trial, we will model the center from which patients are recruited as a fixed effect, thereby mitigating confounding by centers are recruited as a fixed effect, thereby mitigating confounding by center and adjust related to the BASC parent trial, we will model the center from which patients are recruited as a fixed effect, thereby mitigating confounding by center and adjusting variance estimates for clustering of participants within centers.

Our analyses to rule out undue and unjust inducements entail three primary covariates: risk perception, annual household income, and economic well-being. All models will use enrollment in the parent trial as the outcome. To determine if incentives represent undue inducements for research participation, we will test the statistical interaction between incentive size and the primary covariate of risk perception on

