the outcome of enrollment in the parent trials. We will test two interactions, each in a separate model to avoid collinearity, to determine if incentives represent unjust inducements: that between incentive size and the primary covariate of annual household income, and that between incentive size and the primary covariate of economic well-being. All analyses will be stratified by parent study.

Analyses of interaction terms will be structured as tests of non-inferiority. The null hypothesis, for both trials, will be that the use of incentives meets criteria for undue or unjust inducement. We can reject the null, and conclude the absence of undue or unjust inducement, if the interaction terms are "small" according to pre-specified criteria (in technical terms, the inferiority margin). Said a different way, our analyses are designed to determine if we can exclude the possibility that incentives represent undue or unjust inducements if the resulting interaction terms are sufficiently small. Specifically, we will use one-sided alpha levels of 0.05 to exclude, with 95% confidence, the possibility that any of these interaction odds ratios are >2.0.

We will explore temporal trends in incentives' effects over the study period using stratified analyses. If temporal trends are noted, as may occur if prospective patients learn of the incentives used in these studies, we will adjust for their influence by entering time as a covariate, modeled as a spline. We will evaluate potential effect modifiers (variables in Table 1) using stratified analyses. If differences among strata appear, we will formally test their corresponding interactions with the incentive amount.

TABLE 1 FACTORS FOR ADJUSTMENT AND EXPLORATION OF EFFECT MODIFICATION

Potential factors for adjustment			
Patient level covariates	Variable coding or definition		
• Age	Continuous		
• Gender	Binary		
• Race	Categorical		
Marital status	Categorical		
Education	Categorical		
Income	Categorical		
Economic well-being	Categorical		
Prior research participation	Categorical		
Attitudes towards research:	Continuous, measured using the Research Attitudes Questionnaire-7 (RAQ- 7).		

6. Secondary analysis

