The target enrollment of 576 patients in each RETAIN sub-trial was determined based on the primary goal of ruling out the possibility that incentives represent an undue inducement. Statistically, the presence of an undue inducement is represented by the interaction term between incentive amount and risk on the outcome of enrollment in the parent trial. Thus, we seek to rule out the possibility that the odds ratio associated with this interaction term is appreciably greater than a null value. To facilitate such a power estimation, we considered groups of participants with greater or less than the median level of risk perception who will be randomized to the highest incentive versus the lowest incentive. With an overall sample size of 576 participants in each parent study involved in the RETAIN trial, we assumed that 192 participants would be randomized to each of the 3 incentive arms. Assuming that randomization balances the incentives distribution within each risk-perception group, 96 participants will be assigned to each of the 3 incentives within both the high and low risk-perception groups. Among patients assigned to receive \$0, we set the OR contrasting the odds of enrollment between riskperception groups to 1, such that the OR for those assigned to receive the highest incentive (\$300 or \$500, in MOVE IT and BASC, respectively) represents the interaction odds ratio. We assume a true interaction OR of 1, and use a one-sided significance level of 0.0427 such that the upper 95.73% confidence limit on the observed OR falls entirely below the non-inferiority threshold. If the enrollment rate in the parent trials is 50%, we will have at least 80% power to rule out undue inducement, as represented by an interaction odds ratios of 2.0 or greater. However, because we will actually analyze risk as a continuous variable and incentive size as a 3-level variable, our true power will be greater than the estimates reported here. Similar analyses suggest similar levels of power to rule out the unjust inducement interaction terms.

8. Data Safety & Monitoring Board (DSMB)

We have chartered a DSMB to monitor RETAIN, with purview over both embedded trials, for the expressed purpose of evaluating evidence of undue or unjust inducement. Any serious adverse events, protocol deviations/violations, and unanticipated events will be reported to the IRBs with oversight of recruiting sites, the DSMB, and The National Cancer Institute.

9. Stopping Rules

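### Final SAP 5.c tests interaction odds ratios against 2.0 without incentive scores or moderator units, and the 80% power claimed for 2.0 in 7.b does not follow from that section's own inputs.

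*Combined protocol and SAP*

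**What the plan says.** Final SAP 5.c (Primary analysis) tests three interactions on parent-trial enrolment. One is incentive size by risk perception; another is "that between incentive size and the primary covariate of annual household income"; the third is incentive size by economic well-being. Each is a non-inferiority test whose null is that inducement is present. With one-sided alpha 0.05, the aim is to "exclude, with 95% confidence, the possibility that any of these interaction odds ratios are >2.0".

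On coding, 5.c says "In the above analyses we treated incentive as an ordered variable". Section 6 calls incentive an ordinal factor in the secondary analysis of risk as 0 versus >0. Section 7.b says "we will actually analyze risk as a continuous variable and incentive size as a 3-level variable". Income and economic well-being appear in "TABLE 1 FACTORS FOR ADJUSTMENT AND EXPLORATION OF EFFECT MODIFICATION" as categorical, with no categories, scores or direction.

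Only the power calculation in 7.b attaches a contrast to 2.0, and it does so to make that calculation easier. The groups it compares are those "greater or less than the median level of risk perception who will be randomized to the highest incentive versus the lowest incentive". From 96 patients per cell, 50% enrolment, a true interaction odds ratio of 1 and one-sided alpha 0.0427, it concludes "we will have at least 80% power to rule out undue inducement, as represented by an interaction odds ratios of 2.0 or greater". It adds that true power will be greater, because risk is continuous and incentive has three levels, and that the unjust-inducement terms have similar power.

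Final Protocol 11.c (Stopping Rules) uses 2.0 again, as a bound for the lower confidence limit at the interim tests, also without a unit.

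**The concern.** Ruling out undue and unjust inducement is the trial's primary aim, and the comparison with 2.0 decides it. The number does not fix a hypothesis until the plan says how many units of incentive and of the moderator it spans. Scores 0/1/2, a lowest-to-highest contrast, an orthogonal linear contrast and dollars all give different coefficients from the same data. So do a risk score per point, per standard deviation or by halves.

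The contrast in 7.b could have filled the gap. But 7.b introduces it only for the power estimate and then says the actual analysis will use other codings. Nothing says that the fitted coefficient will be rescaled to that contrast. For income and economic well-being there is not even that much. No direction of coding is given either: if income is coded upwards, the direction of concern lies below 1, where an upper limit of 2.0 does not look.

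The power statement matters for the opposite result. If 2.0 cannot be excluded, a reader who believes in 80% power will take that as more informative than it is.

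**Working it through.** **Inputs from 7.b.** 576 patients per parent trial, 192 per arm, 96 per incentive-by-risk cell, 50% enrolment, true odds ratio 1, margin 2.0, one-sided alpha 0.0427. Section 5.c gives alpha 0.05. The z values are 1.720 (0.0427) and 1.645 (0.05), and ln 2 = 0.693. No covariates or missing data are allowed for.

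**Formula.** Power = Φ(ln 2 / SE − z). The variance of the log odds in a cell of n patients at 50% is 1/(n × 0.25), which is 1/24 for n = 96.

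**1. The stated 80%.**
- Literal 7.b set-up, $0-arm odds ratio taken as known to be 1: SE = √(2/24) = 0.289. Power = Φ(2.401 − 1.720) = **75%** (78% at alpha 0.05).
- Interaction as a model must estimate it, from four cells: SE = √(4/24) = 0.408. Power = Φ(1.698 − 1.720) = **49%** (52% at 0.05).
- Continuous risk on the same contrast, normality assumed: the halves differ in mean by 2√(2/π) = 1.596 SD, so SE = 1.596 × √(2/(192 × 0.25)) = 0.326. Power = Φ(2.126 − 1.720) = **66%** (69% at 0.05).

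So 80% is not reproduced. The gain that 7.b claims for continuous risk is right in direction but not large enough. For 80% power, the four-cell contrast at 0.0427 needs 219 per cell, or 6 × 219 = 1,314 per parent trial. With 576 patients, the odds ratio that can be excluded with 80% power is about 2.85.

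**2. MOVE IT.** The SAP change log (2/17/2020) reports that more than 85% of risk scores in the Ambulation trial, read here as MOVE IT, were 0. A split into halves cannot be formed. For 0 versus >0 with 15% above 0, an arm has 28.8 and 163.2 patients. SE = √(2 × (4/28.8 + 4/163.2)) = 0.572. Power = Φ(1.212 − 1.720) = **31%** (33% at 0.05) if 2.0 is highest versus lowest incentive. A share below 15%, or enrolment other than 50%, lowers it.

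**3. What the missing scale does to the decision.** Suppose the true odds ratio on the 7.b contrast is 2.0, and that contrast spans k coefficient units. Comparing the coefficient with 2.0 then means an effective margin of 2^k, and P(declared absent) = Φ((k − 1) × ln 2 / SE − z). With risk in halves, SE 0.408 and alpha 0.05:

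| Incentive coding | k | Effective margin | P(declared absent) |
|---|---|---|---|
| One unit = lowest to highest | 1 | 2.0 | 5% |
| Orthogonal linear contrast | √2 | 2.7 | 17% |
| Scores 0/1/2 | 2 | 4.0 | 52% |

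The risk unit matters as well. With incentive as highest versus lowest and normal continuous risk, k = 1.596 × (risk SD in units). The probability is 2% at an SD of 0.5 units, 35% at 1 and above 99% at 2. These SDs are assumed, and normality is doubtful given the reported skew, so the figures show sensitivity only.

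For income scored in m ordered categories (m assumed), 2.0 per category is 2^(m−1) from end to end: 8 at m = 4 and 32 at m = 6.

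**4. Scales on which power is high.** At alpha 0.0427, 2.0 per incentive step with risk in halves gives SE = 0.408/2 = 0.204 and power 95%. So does 2.0 per SD of risk, lowest to highest incentive (SE = √(2/48) = 0.204). MOVE IT, 0 versus >0 per step, gives 76%.

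**The case against.** - *The incentive descriptions agree.* A reader might infer that ordered variable, ordinal factor and 3-level variable contradict one another. They do not. They describe one ordered variable, and the change log's remark about a single contrast points to one trend term. Only the scores are missing.
- *The scale can be guessed.* Risk is a nine-item score, so per point is a natural reading. That is fair, but it is nowhere stated, and it would not match the 7.b contrast.
- *Power depends on the scale too.* A reader might infer that no reading reaches 80%, or that MOVE IT cannot exceed 31%. The documents do not support either without the condition that 2.0 is highest versus lowest incentive on the stated risk split. Step 4 shows 95% and 76% on other scales. Those scales reach it by testing a wider margin than 7.b describes, such as 4.0 end to end.
- *The literal shortfall is small.* On 7.b's own simplification it is about 5 points (75% against 80%). The 49% comes from also counting the sampling error of the $0 arm, which the planned interaction model cannot avoid.
- *The MOVE IT distribution came later.* The power text is unchanged from the Original SAP, finalised before enrolment in these two trials. The clumping at 0 is therefore not an error in the calculation when made, and the sponsor answered it with influence diagnostics and the binary analysis. It does mean that the text no longer describes the trial.
- *Low power is safe here.* Because the null is that inducement exists, low power cannot by itself produce a false claim of absence. This stands. The false-claim risk comes from the undefined scale; the power error affects how a failure to exclude 2.0 is read.

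**Conclusion.** Both parts hold. The scale of the 2.0 margin is undefined for all three moderators, and the coding choice alone can move the chance of wrongly declaring no inducement from 5% to 52% with risk in halves. The at-least-80% figure does not follow from 7.b's contrast and inputs: 75% on its literal reading, 49% with four estimated cells, and 66% for continuous risk if that is normal. On the highest-versus-lowest scale, MOVE IT risk as 0 versus >0 gives at most about 31%.

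The power figures rest on normal approximations, 50% enrolment and no missing data. The error-rate illustrations also assume a particular coding or risk SD. A reader might infer that the trial's actual conclusion was wrong, or biased towards absence. The documents do not show this: the scores actually used are not given, and the effective margin could be stricter or looser than 2.0. Since the rule decides the primary aim, it should be corrected before results are interpreted.

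**What to change.** In 5.c:
- State the incentive scores, and define 2.0 as the highest-versus-lowest incentive interaction odds ratio, tested as a linear contrast of the fitted coefficients.
- Name one moderator contrast for each test. Options are above versus below the median risk score, or its continuous equivalent, in BASC; 0 versus >0 in MOVE IT; and lowest versus highest category for income and for economic well-being.
- Orient every contrast so that the direction of concern is above 1.
- Use one alpha, reconciling 0.05 (5.c) with 0.0427 (7.b).

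State the same scale for the 2.0 bound in Final Protocol 11.c. Label all of these choices as made after interim risk distributions were seen.

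In 7.b, replace the 80% claim with the power for the chosen contrasts (about 49% for its own four-cell contrast at 0.0427), and say that failure to exclude 2.0 is inconclusive.

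The cost is SAP wording, one contrast statement per model and a rewritten power paragraph, with no extra patients or data. The downside is a less favourable stated power and a margin scale that must be reported as post hoc.

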As a result of both the successes of the Phase II and Phase III collaborations, and the shortcomings of the Phase I 1308 collaboration, the RETAIN team decided to end our collaboration with 1308 and focus all resources squarely on the Phase II and Phase III collaborations. This decision was discussed with the 1308 investigators on November 27 and the RETAIN team received approval to move forward exclusively focused on Phases II and II from the sponsor, the Nation Cancer Institute, on November 30, 2017.

As a result of this change, the team removed RTOG 1308-relevant language from the IRB protocol and ended Penn's oversight of the RETAIN trial at MDACC, a relying institution. The MGH and Washington University research teams closed out the RETAIN study at their respective sites.

7. Approved January 25, 2018

a. Phase II – Modification to BASC screening procedures

The study teams for BASC and RETAIN implemented a RETAIN-related change to the phone screen script being used at Northwestern and Penn. For patients randomized to RETAIN, the team stopped asking, "Does this sound like something that you are interested in?" before administering the RETAIN surveys. They simply transitioned from introducing the study basics to administering the RETAIN questions by saying, "Now we ask that you answer a few more questions before finalizing the details of your intake visit."

The goal of this change was to provide an opportunity to capture RETAIN baseline data that was not being collected systematically due to early withdraws from the phone screen call.

b. Phases II and III - Revisions to the Compared Riskiness Scale

The study team examined the phrasing for the Compared Riskiness scale in an Amazon mechanical Turk study aimed at countering floor effects in our measure of risk perception. As a result of this investigation we made several changes to the phrasing of the questions in the scale. We did not add new items to the scale.

8. Approved February 21, 2018

a. Phase II – Modification to MOVE IT recruitment procedures

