This modification was submitted in tandem with our colleagues on the Mobility, Outcomes, and Validated Experiences Incentive Trial (MOVE IT) study (IRB # 823491). With this change MOVE IT eligibility was assessed earlier in the enrollment process order to randomize and announce the incentives earlier to patients. We also added a note to patients randomized to the \$100 and \$300 arms that they can receive the first installment of their payment the day they decide to participate. We modified the modality of payments such that the first payment would be administered via ClinCard to ensure that all patients who enroll can go get the first installment in a non-check format. These changes were reflected in the updated debriefing and consent forms.

b. Phases II and III – Modifications to the Compared Riskiness Scale

We also updated the Compared Riskiness scale once more in an effort to counter early floor effects.

9. Approved April 23, 2018

a. Phase III – Modification to data collection and administration of surveys

In our modification approved February 21, 2018, we moved the randomization to 1 of 3 incentives to earlier in the clinical research coordinators' recruitment script to optimize the research team's ability to augment enrollment in the MOVE IT study. Patients who are randomized in this model become RETAIN subjects, and we had a way to capture demographic information on RETAIN subjects who decline participation in MOVE IT. However, we did not have a means of capturing risk perception data on patients who declined early, before reading the consent form for MOVE IT. To mitigate the issue of data missingness among these patients and to ensure we were able to execute the study successfully, we decided to include the Compared Riskiness survey in the baseline set of surveys, as well as include a minimal description of risks and benefits early in the enrollment script. This modification and change in data collection allowed us to test the interaction between incentive size and risk perception on the outcome of enrollment – and detect undue inducement, a key outcome of the study and criterion for the Data Safety and Monitoring Board to consider stopping the trial.

10. Approved January 25, 2019

a. Phase III – Addition of Qualitative Evaluation of Patient Decision-Making

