During the debriefing session, the parent trial staff will explain that all RETAIN- and parent trial-enrolled participants will receive the full high-level incentive payment (\$300 in BASC (see Section 6.d.), and \$300 in MOVE IT) in two installments. Such payment equalization is necessary because it promotes fairness by rewarding people equally for making equal contributions to the parent RCTs.

7. Randomization

a. Groups

Subjects enrolled in RETAIN will be randomized into three groups. Depending on which group they've been assigned, subjects will be presented with one of three parent trial consent forms in both electronic and paper formats (see Section 8 Study Procedures). The parent trial consent forms will display three different incentive amounts (low-, middle-, or high-level incentive). Consent 1 (low-level incentive arm) will include a paragraph on the first page that will briefly state what the study is about and indicate to patients that participation in the study is voluntary and patients will not be paid if they choose to participate. The consent form will indicate that participants will not be paid under the standard section, "Will I be paid for taking part in this study?" Consents 2 (middle-level incentive arm) and 3 (high-level incentive arm) will include a paragraph on the first page that will briefly state what the study is about and indicate that participation is voluntary and patients will be paid the incentive (middle- or high-level) incentive arm) will include a paragraph on the first page that will be paid the incentive (middle- or high-level) if they choose to participate. The consent form will also include payment information under the

standard section, "Will I be paid for taking part in this study?" that describes the level. Consents 2 and 3 will also include information regarding the impact on compensation if patients stop taking part in the study under the standard section (BASC). During debriefing, all participants enrolled in RETAIN and their respective parent trials will learn of their assignment to one of three groups.

b. Assignment

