- Tests two behavioral interventions in combination with Varenicline in a population of daily smokers with current or lifetime major depressive disorder
- Eligible patients are randomized to receive inform consent forms offering \$0, \$200, or \$500 incentives for participation
- Patients are enrolled at The University of Pennsylvania and Northwestern University; randomization is stratified by site

b. MOVE IT Trial

- The Mobility and Outcomes for Validated Evidence Incentive Trial (MOVE IT) (NCT 03321279)
- Aims to examine the impact of a supportive social incentive-based gamification intervention in the three months post-hospital discharge among general medical and cancer patients using wearable technology
- Eligible patients are randomized to receive inform consent forms offering \$0, \$100, or \$300 incentives for participation
- Patients are enrolled at the Hospital of the University of Philadelphia by a team of clinical research coordinators; randomization is stratified by clinical research coordinator
- By necessity, clinical research coordinators administering the consent process in both parent trials are unmasked to the incentive information being messaged to prospective participants. The introduction to the study and the informed consent process have been robustly scripted for research staff involved in both trials to ensure that messaging is consistent and biases are minimized.

4. Population

Eligibility for RETAIN is contingent on eligibility for the BASC and MOVE IT parent trials.

- Adults age 18 years or older who are daily smokers with current or lifetime major depressive disorder without psychotic features (BASC)
- Adults age 18 years or older who are admitted for inpatient care to the Hospital of the University of Pennsylvania (HUP) on medicine or oncology floors (MOVE IT)

Patients randomized to RETAIN must be:

- Eligible for parent RCT
- 18 years or older
- English-speaking

In the BASC trial, prior knowledge of the incentive randomization or payment equalization used for this

study, which will be assessed with open-ended prompts during the first encounter, is an exclusion criterion. We will not assess for prior knowledge in the inpatient MOVE IT study population. However, only one patient per hospital room will be approached for the MOVE IT study to protect against contamination.

5. Primary outcome and analytic method

a. Primary outcome

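### Final SAP 5.c: a spline main effect for time cannot correct an incentive effect that changes over the study; time interactions are needed as a prespecified sensitivity analysis

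*Combined protocol and SAP*

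**What the plan says.** Three sentences in Final SAP 5.c (Primary analysis) matter.

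- Detection: "We will explore temporal trends in incentives' effects over the study period using stratified analyses". No threshold or formal test is given.
- Remedy: if trends appear, "as may occur if prospective patients learn of the incentives used in these studies", then "we will adjust for their influence by entering time as a covariate, modeled as a spline". No product of time with incentive, or with any inducement interaction, is named.
- Other modifiers: "We will evaluate potential effect modifiers (variables in Table 1) using stratified analyses". Where strata differ, the corresponding interaction with incentive is to be tested formally. Time is not in Table 1.

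The same section tests three interactions with incentive (risk perception, household income, economic well-being). Each is a non-inferiority test against an OR of 2.0 at one-sided 0.05.

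Background facts:

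- Under Final Protocol 6.e, all enrolled "participants will receive the full high-level incentive payment", whatever their arm.
- BASC excludes anyone with "prior knowledge of the incentive randomization or payment equalization used for this" trial (Final Protocol 6.c). MOVE IT does not ask; it relies on limiting approaches within a room and not re-approaching readmitted patients.
- Changes to Protocol, item 8.a (21 February 2018), records that MOVE IT patients in the $100 and $300 arms were now told "they can receive the first installment of their payment the day they decide to participate".

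**The concern.** A trend in an effect is an interaction with time. The SAP looks for exactly that, then prescribes a term that represents something else. For Table 1 modifiers the same paragraph prescribes the right tool. The modifier it singles out as possible contamination does not get it.

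The direction matters. A patient who knows that everyone ends up with the top amount no longer faces a $0, middle or high offer. Contrasts between arms then shrink, and interactions with incentive may shrink with them. The inducement tests succeed when the interaction is small, so dilution of an interaction favours the conclusion sought. A report could say that contamination had been adjusted for while any such dilution remained in the estimate.

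The dated MOVE IT change is a separate reason why effects may vary over time. It altered the offer in the paid arms only, and a smooth main effect of time cannot represent that either.

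**Working it through.** **1. Structure.** The SAP model with its remedy is logit P(consent) = b0 + b1·A + b2·X + b3·A·X + s(t), with A the incentive, X the covariate and s(t) the spline. Here b3 is one number for the whole study. If the true value is b3(t), the fit returns roughly its average. Blocks of 3 and 6 (Final SAP 3) keep t nearly independent of A, so s(t) has little to act on.

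**2. Standard error, from the plan's own power figure.** Final SAP 7.b gives at least 80% power with 96 per cell, 50% enrolment, true OR 1, margin 2.0 and one-sided alpha 0.0427. I used power = Φ(ln 2/SE − z).

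- Two cells: SE = √(2/(96×0.25)) = 0.289; power Φ(0.693/0.289 − 1.720) = 75.2%.
- Four cells (the full interaction): SE = √(4/(96×0.25)) = 0.408; power 49.1%.

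Neither reproduces 80%. That is a separate matter; I need only the SEs here. The four-cell SE is the relevant one, because an interaction compares two ORs.

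**3. Effect of dilution.** Let the undiluted interaction OR equal the margin, 2.0, and let the log OR be diluted on average by a fraction f (assumed). The pooled OR is 2^(1−f), and the false non-inferiority rate is Φ(f·ln 2/SE − 1.645).

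| f | Pooled OR | Four-cell SE | Two-cell SE |
|---|---|---|---|
| 0 | 2.00 | 5.0% | 5.0% |
| 10% | 1.87 | 7.0% | 8.0% |
| 25% | 1.68 | 11.1% | 14.8% |
| 50% | 1.41 | 21.3% | 32.8% |

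Example: f = 50%, four cells: Φ(0.347/0.408 − 1.645) = Φ(−0.796) = 21.3%. At alpha 0.0427 the four-cell rates for 10%, 25% and 50% are 6.1%, 9.8% and 19.2%.

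**4. Does the spline help?** Large-sample logistic fits assumed a first-half interaction OR of 3.0, a first-half high-versus-low incentive OR of 2.25, and second-half log effects multiplied by 0.5, 0.25 or 0.

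| Second-half multiplier | Interaction OR, no time → spline | Incentive OR, no time → spline |
|---|---|---|
| 0.5 | 2.25 → 2.25 | 1.83 → 1.83 |
| 0.25 | 1.94 → 1.95 | 1.64 → 1.65 |
| 0 | 1.69 → 1.70 | 1.48 → 1.49 |

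Adding period interactions recovers 3.0 and 2.25.

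**5. Simulation of contamination.** Contaminated patients behave as if offered the top amount. Arms are scored 0, 0.5 and 1, risk is binary, and the undiluted interaction OR is 2.0. ORs are from n = 600,000. False non-inferiority is from 1,500 trials of N = 576 at one-sided 0.05 (Monte Carlo error near 5%: √(0.05×0.95/1500) = 0.6 points).

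| Contamination, rising linearly from 0 | Model | Interaction OR | False non-inferiority |
|---|---|---|---|
| to 50% | no time | 1.70 | 11.1% |
| | spline main effect | 1.70 | 11.1% |
| | time interactions, at study start | 1.98 | 4.5% |
| to 100% | no time | 1.45 | 19.6% |
| | spline main effect | 1.46 | 19.0% |
| | time interactions, at study start | 2.07 | 4.3% |

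If contamination arrives as a step, the linear time-interaction model overshoots at study start (OR 2.46). That is a reason to report by period as well.

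**6. Contrary scenario.** If only the main incentive effect fades (by up to 50%) and the interaction is constant, the spline model gives OR 1.99 and false non-inferiority of 4.4%: no bias. For stronger fades of this kind only the large-sample OR was obtained, and it stays at 1.99.

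**7. Precision by period.** Half the trial has 48 per cell: SE = √(4/(48×0.25)) = 0.577. With a true OR of 1, power to exclude 2.0 is Φ(0.693/0.577 − 1.645) = 33%.

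**The case against.** The strongest reply is that the harm is hypothetical and partly guarded against.

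- The documents give no contamination rate. BASC screens out prior knowledge, MOVE IT limits approaches within a room, and Final Protocol 8.g says decliners are not debriefed. This stands. It makes the bias conditional and leaves MOVE IT as the more exposed trial.
- The SAP already plans a time-stratified look at incentive effects, so a fade would be visible. This stands in part. The look is exploratory, does not explicitly cover the three inducement interactions, and is not linked to their tests.
- The interaction need not fade with the main effect, and if it does not there is no bias. This stands (step 6). However, Final Protocol 8.g itself argues that disclosing the randomization would defeat measurement of both intended and unintended consequences.
- The MOVE IT same-day-payment note would plausibly strengthen later effects, not weaken them. This stands, so it is no evidence of a fade. It is still a dated change in the effect that a time main effect cannot capture. The January 2018 change to the BASC phone script did not alter the offer and is no reason for a cut-point.

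A reader might infer from step 4 that a true early interaction of 3.0 would be passed as non-inferior because the pooled OR is below 2.0. The SAP does not support that, since its claim rests on the upper confidence limit. With SE 0.408, pooled ORs of 1.95 and 1.70 have upper limits of about 3.8 and 3.3 (1.70 × e^(1.645×0.408) = 3.3). The chance of a false claim is about 6% and 11%.

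**Conclusion.** The stated remedy does not do what the SAP says it does. That follows from the model and the blocked allocation, and the fits agree: the spline moves the ORs by about 0.01.

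The consequence for the non-inferiority tests is conditional. It needs real contamination and an inducement interaction that itself fades. Under those assumptions, with an undiluted OR at the margin and the four-cell SE, false non-inferiority rises from 5% to about 7%, 11% or 21% for mean dilution of 10%, 25% or 50%. The dilution levels, the effect sizes and the 0/0.5/1 scoring in the simulations are my assumptions.

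A reader might go further and conclude that the trial is biased toward finding no inducement. The documents do not show that: they report no contamination, and they describe safeguards. The point is a wording and specification fault in Final SAP 5.c that should be corrected, chiefly for MOVE IT.

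**What to change.** In Final SAP 5.c, replace the spline sentence with text to this effect:

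- If a trend in the incentive effect is noted, fit incentive × time as a prespecified sensitivity analysis. In the three inducement models, also fit covariate × time and incentive × covariate × time.
- Report the incentive effect and each interaction OR by period beside the pooled non-inferiority test: early versus late in both trials and, in MOVE IT, before versus after 21 February 2018.
- If a spline main effect is kept, describe it as adjusting for drift in overall consent, not for contamination.

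The cost is SAP wording and a few model terms. The real price is precision: half the sample has about 33% power to exclude an OR of 2.0 when the true value is 1, and the documents do not say how many MOVE IT patients were randomized before the February 2018 change. The period results should therefore inform how the pooled result is read. They should not be made a condition for claiming non-inferiority.
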